Although critical to the pathogenesis of the most important illnesses in children (both local and systemic) little is known about the microbiome of the nasopharynx in health or disease. Investigation of the inhabitants of the nasopharynx using conventional microbiologic techniques provides incomplete information; corresponding studies of the gastrointestinal tract indicate that more than 90% of colonic microbes are not detected by culture-based techniques.¹² The advent and current availability of culture-independent microbial profiling approaches such as high-throughput sequencing or the 16S rRNA PhyloChip provide much needed tools to define the diversity of the nasopharyngeal microbiome. The PhyloChip is a DNA-based microarray that permits identification of approximately 8,500 types of bacteria or taxa (defined as groups of bacteria that exhibit at least 97% sequence identity at the 16S rRNA sequence level) in a single parallel assay. Compared with species-specific qPCR approaches or laboratory culture, this tool, due to its ability to detect the presence and relative abundance of 8,500 taxa in parallel, provides substantially improved ability to detect species present in the human microbiome. Compared with next-generation sequencing which, depending on the depth of sequencing performed, may only provide information on the most highly abundant species present, the PhyloChip can detect rare members of the community as efficiently as the dominant species, essentially providing a cross-sectional profile of community composition. This latter ability is key to understanding the etiology of idiopathic diseases, including chronic rhinosinusitis (CRS), which, as we demonstrate in preliminary data, is highly dependent on the composition of the microbiota. Thus, by determining the presence, absence and relative abundance of approximately 8,500 taxa under standardized conditions in each sample, the PhyloChip represents an economical approach for providing a high-resolution, cross-sectional profile of the community present. Further, as we demonstrate in preliminary data, due to our ability to normalize the large datasets generated by this method, it is possible to apply robust statistical tools to characterize microbiota and identify lead candidates for disease etiology. We have used these features to characterize the nasopharyngeal microbiota in adult populations,¹⁵ as well as to define a novel etiology for adult CRS (Abreu et al, in review; see preliminary data p.8). Hence, **application of this tool to investigate relationships between the composition of the nasopharyngeal bacterial community and the risk of developing sinusitis provides an outstanding opportunity to address questions of fundamental clinical importance. Which bacteria comprise the normal nasopharyngeal microbiome in pediatric patients, and which individual host characteristics and environmental exposures influence these communities? Do infections with specific respiratory viruses alter the composition of the nasopharyngeal microbiome thereby impacting bacterial community reassembly and promoting sinusitis? Are there salutary elements of the nasopharyngeal microbiome that can prevent the progression of URI to acute bacterial sinusitis?** Description of the nasopharyngeal microbiome in healthy children is a first step to testing the therapeutic potential of manipulating the nasopharyngeal microbiome in viral URI by either inhibiting pathogenic bacteria or promoting colonization by protective species.

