- We will enroll and follow eligible children between ≥ 4 through < 8 years of age prospectively for one year. Using high-throughput multiplex PCR-based viral diagnostics, the identities of antecedent viral infections will be determined for each symptomatic URI, and during four surveillance periods. We hypothesize that rhinovirus will be the most common viral URI to predispose to acute bacterial sinusitis. This information can potentially direct the development of antiviral medication or viral vaccines.
- Using stringent clinical definitions for acute bacterial sinusitis, we will determine the incidence of sinusitis as a complication of viral URI. This has not been previously determined

and we hypothesize that sinusitis will complicate viral URI in 8% of cases in these young children.

Aim 2: To define relationships between the nasopharyngeal microbiome, viral illnesses, and progression to clinical sinusitis.

Nasopharyngeal samples and a pilot number of stool samples obtained before, during and after viral respiratory infections will be analyzed for bacterial species using array-based diagnostics (PhyloChip) and conventional semi-quantitative microbiologic techniques in two groups of children:

- a) those with viral URIs that resolve spontaneously and
- b) those whose URI progresses to acute bacterial sinusitis.

We hypothesize that the presence and density of sinopathogens and inhibitory commensal microbiota, together with modifications caused by infection with common respiratory viruses, will influence the likelihood of progression to acute bacterial sinusitis. Knowledge of these predictive elements will direct preventive strategies and treatment decisions.

The primary objectives of the study are as follows:

1. To determine a) the incidence of acute bacterial sinusitis in children ≥ 4 through < 8 years of age as a complication of an antecedent viral URI, b) if certain viruses are more likely than others to precipitate an episode of bacterial sinusitis and c) what percentage of sinus infections are, in fact, preceded by viral infection.

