e) Study methods - processing and interpreting the PhyloChip data. Detection and quantification criteria for each taxon detected by the PhyloChip will be conducted as described previously using a positive fraction threshold of ≥ 0.90 .²¹ Statistical analyses using log-transformed fluorescence intensities will be performed in the R environment (www.R-project.org), using the ecological community analysis package *vegan* [version 1.16-1; (129)] to calculate metrics of bacterial community composition, including richness (number of bacterial types present), evenness (relative distribution of species in a community) and diversity (index based on both richness and evenness metrics). Bray-Curtis dissimilarity measures of ecological distance will be calculated before performing non-metric multi-dimensional scaling, a nonparametric ordination method that maps community relatedness based on species presence and abundance. This approach will be used to assess variability in bacterial community structure (particularly to examine if a distinct community composition is associated with differential sinusitis outcomes). Between-group differences (e.g. sinusitis vs no-sinusitis) in both gross community metrics (e.g. richness, evenness and diversity) as well as taxon abundance will be determined by two-tailed *t*-testing or ANOVA and adjusted for false discovery using *q*-values, as we have recently described.¹⁴ Taxa exhibiting *p*- and *q*-values < 0.05 , will be considered statistically significant. Correlation analysis of taxon abundance against that of key sinonasal pathogens (both bacterial and viral) will be performed using the *multtest* package available as part of the Bioconductor suite of analysis programs²² to determine relationships between these species and relative abundance of all other taxa detected. All data will be maintained on a secure server in the Department of Medicine at UCSF, only accessible to those individuals involved in the study. Sequence data generated by 454-pyrosequencing will be used to validate 16S rRNA PhyloChip findings as we have previously described.²³

[figure not shown]
f) Study methods – Conventional bacteriology of nasopharyngeal swabs. Half of the nasopharyngeal swab will be submitted for routine bacterial cultures to the CLIA certified microbiology laboratory of the University of Wisconsin Hospital and Clinics. The plates will be interpreted semi-quantitatively. Isolates of *S.*

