To estimate the incidence of acute bacterial sinusitis as a complication of URI we will use a random effects generalized linear model assuming binomial distribution. We expect a total of 1500-1800 episodes of URI among the children and hypothesize that ABS will complicate 8% of these cases resulting in approximately 120 cases of acute bacterial sinusitis. If the true percent of viral URIs progressing to acute bacterial sinusitis is 8% then 1500 cases will give us 80% power to estimate the incidence with a 95% confidence interval no longer than 2.9%. If we were to observe exactly the 8% incidence the 95% confidence interval would be (6.68%, 9.49%).

Aim 2 - The episodes of acute bacterial sinusitis and uncomplicated URI chosen for PhyloChip analysis will be from two groups. The “acute bacterial sinusitis group” will consist of the first episode of acute bacterial sinusitis occurring among 50 randomly selected children who have one or more episodes of acute bacterial sinusitis. Only the first episode will be eligible to avoid data clustered within child. To avoid running all the PhyloChip analysis at the end of the study we will select the children in groups of 10 evenly spaced over the 52-months of enrollment and follow-up. An additional 50 matched control cases of uncomplicated URI will be selected (10 at a time) from the group of children who have not yet had an episode of acute bacterial sinusitis. The controls will be chosen so that their uncomplicated URI closely matches the case of acute bacterial sinusitis in calendar time. If a control child later develops acute bacterial sinusitis, the control child will become eligible to be chosen for the acute bacterial sinusitis group. If this occurs a different matched control will be chosen as a replacement. This process will result in a few extra PhyloChips being run but is necessary as the processing of PhyloChips is time consuming and cannot be delayed until the end of the study. In addition, the surveillance sample most closely preceding the episode of acute bacterial sinusitis and uncomplicated URI will also be analyzed using the PhyloChip.

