Regression analyses will be used to assess relationships between progression to acute bacterial sinusitis, demographic variables (including age, gender, attendance at daycare, family or personal history of asthma, pets, etc.), season and gross metrics of bacterial community composition (richness, evenness, and diversity indices) as well as the relative abundance of all taxa detected (including sinopathogens), to determine if these variables are related to specific features of the nasopharyngeal microbiota. A term will be included to account for the paired structure of the data. For each of the continuous predictors, a difference in the mean values between the acute bacterial sinusitis group and the control group equal to 50% of the variability of that predictor will give us greater than 80% power to find a significant effect of the predictor. For predictors which take values of yes or no (such as presence of a sinopathogen), we will have 80% power to detect the difference between the percent of sinopathogens present equal to 55% for the acute bacterial sinusitis group and 30% for the control group.

PhyloChip outcomes including richness, evenness and diversity indices of the nasopharyngeal microbiome sample obtained during each of the 50 episodes of acute bacterial sinusitis will be compared to those obtained during the most recent surveillance period by using paired t-tests. Differences in specific taxon abundance in these two samples will be determined by paired t-test and adjusted for false discovery.

Correlation analysis of the abundance of each individual taxon against that of key sinonasal pathogens (both bacterial and viral) will also be performed to determine relationships between these species and relative abundance of all other taxa detected. Hierarchical cluster analysis will be used to display similarity of microbiota among nasopharyngeal samples.

The pilot stool sample size is based on the base sample size of 12 per group when no prior information is available (Julious, 2005). We propose to double that number to ensure enough samples over the seasonality of the one year enrollment. This feasibility is based on our average enrollment of 7 subjects per month and if 20% join the sub-study (1-2 per month), enrollment would take about 12 months including family members.

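### Array abundance of the three named sinopathogens is judged by the taxon-wide q-value rule, while the power claimed for it makes no allowance for multiple testing

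*Protocol*

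**What the plan says.** The Aim 2 hypothesis in the Protocol (Approach, Overview) begins: "We hypothesize that the presence and density of sinopathogens and inhibitory commensal microbiota". The Significance section and the conventional bacteriology methods (4.f) identify the sinopathogens as *S. pneumoniae*, *H. influenzae* and *M. catarrhalis*.

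The section on processing PhyloChip data (4.e) compares taxon abundance between groups, giving sinusitis versus no sinusitis as its example, by two-tailed tests with false-discovery adjustment. Taxa whose p- and q-"values < 0.05 , will be considered statistically significant". No taxon is set apart. According to the Significance section, the array "permits identification of approximately 8,500 types of bacteria or taxa".

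For Aim 2, Data Analysis (4.i) takes the "first episode of acute bacterial sinusitis occurring among 50 randomly selected children". It continues: "An additional 50 matched control cases of uncomplicated URI will be selected". The regression predictors include community metrics "as well as the relative abundance of all taxa detected (including sinopathogens", and "A term will be included to account for the paired structure of the data". For each continuous predictor it claims more than 80% power when the group means differ by 50% of that predictor's variability. For yes/no predictors such as presence of a sinopathogen the claim is 80%, with this as the assumed effect: "difference between the percent of sinopathogens present equal to 55% for the acute bacterial sinusitis group and 30% for the control group". Neither power statement gives an alpha or mentions multiplicity.

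**The concern.** A q-value rule suits a screen of many taxa with no prior claim on any of them. Three species named in the hypothesis before any data are seen are a different case. Under one taxon-wide rule, the cut-off that a named pathogen must meet is set by how many unrelated taxa happen to differ. A reader of Data Analysis would expect more than 80% power for a 0.5 SD difference in sinopathogen abundance, but the rule in 4.e may deliver much less. At stake is a real difference in pathogen density, between URIs that progress and URIs that resolve, being reported as non-significant in a comparison that the Protocol describes as well powered.

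**Working it through.** **Inputs.** From the Protocol: 50 sinusitis episodes and 50 matched controls; two-tailed tests; p and q below 0.05; a difference of 50% of variability, read here as 0.5 SD. Assumed, because the Protocol does not give them: the within-pair correlation ρ (0 to 0.5) and the share π of taxa that truly differ (1% to 30%). One value of π, 17.4%, is 1,482/8,500. The 1,482 is the number of taxa significantly lower in chronic rhinosinusitis in the preliminary data (4.h.ii), and 8,500 is the array's capacity.

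**The Protocol's own figure.** For an unpaired comparison, 0.5 × √(50/2) = 2.5.
- Two-sided 5%: Φ(2.5 − 1.96) = 70.5% (69.7% by noncentral t).
- One-sided 5%: Φ(2.5 − 1.645) = 80.4%.
- Paired, two-sided 5%: standardised difference dz = 0.5/√(2(1 − ρ)), noncentrality dz√50, 49 degrees of freedom. Power is 69%, 81%, 83% and 93% at ρ = 0, 0.25, 0.3 and 0.5.

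So the claim is met by a single unadjusted test that is one-sided, or two-sided with ρ of about 0.25 or more. Section 4.e specifies two-tailed testing.

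**Power under the q-rule.** Let t be the per-taxon p cut-off and power(t) the paired noncentral-t power at t. If every truly differing taxon differs by 0.5 SD, the cut-off that gives a 5% false discovery rate solves

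(1 − π)t / [(1 − π)t + π·power(t)] = 0.05.

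Example with ρ = 0 and π = 10%: t = 0.00106 and power(t) = 0.182. Check: 0.9 × 0.00106 = 0.00095; 0.1 × 0.182 = 0.0182; 0.00095/(0.00095 + 0.0182) = 0.05.

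**Power for one sinopathogen taxon, 0.5 SD, 50 pairs**

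| Rule | ρ = 0 | ρ = 0.3 | ρ = 0.5 |
|---|---|---|---|
| Single test at 0.05 | 69% | 83% | 93% |
| q-rule, π = 1% | 1% | 10% | 32% |
| q-rule, π = 5% | 9% | 30% | 58% |
| q-rule, π = 10% | 18% | 43% | 70% |
| q-rule, π = 17.4% | 29% | 55% | 78% |
| q-rule, π = 30% | 43% | 68% | 86% |
| Family of three, at 0.05/3 | 51% | 69% | 85% |

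The last row is the strictest Holm step, so it is a lower bound for Holm. The Benjamini-Hochberg cut-off, t = 0.05[(1 − π)t + π·power(t)], is slightly stricter: at ρ = 0.5 it gives 76% and 82% in place of 78% and 86%. The separate family has more power in every cell except π = 30% with ρ = 0.5, where the two are about equal.

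**The case against.** Five points against the concern carry weight.

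- **Other routes to the hypothesis.** Presence of a sinopathogen is a yes/no predictor with its own power statement, and the three species are also measured by semi-quantitative culture outside the array. The Protocol attaches no q-rule to either. A reader might infer that the Aim 2 sinopathogen hypothesis as a whole has little power. The documents do not support that: only array abundance is affected.
- **Breadth of Aim 2.** The hypothesis also covers inhibitory commensals and viral modification, and the second primary objective covers community diversity. A taxon-wide screen serves those, so the q-rule is not wrong in itself.
- **The link between sections is an inference.** The regression sentence in 4.i does not state the q-rule. The rule comes from 4.e, where it covers taxon abundance between groups. That is the natural reading, since 4.e uses sinusitis versus no sinusitis as its example, but 4.i does not say so.
- **Size of the loss.** A reader might also infer that 8,500 taxa by themselves make a non-significant result the usual outcome. They do not. The cut-off adapts to the share of taxa that differ, 8,500 is array capacity rather than the number detected, and power is high when signal is dense and pairs are well correlated. The only density figure in the Protocol comes from 7 versus 7 maxillary sinus samples in chronic rhinosinusitis, a different site and disease, so it settles little.
- **The remedy.** Array taxa are groups defined by sequence identity, and the Protocol does not map three species to exactly three taxa. A separate family also does not reach 80% at low correlation.

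It could be said, too, that the choice of families belongs in a statistical analysis plan. Here, though, the Protocol already fixes both a rule and a power figure, and the two do not agree.

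**Conclusion.** The concern holds for PhyloChip relative abundance of the three named sinopathogens and no further. That comparison is judged by the rule used for every detected taxon, while the power claimed for it makes no allowance for multiplicity. At correlation 0.25, where the two-sided unadjusted test just reaches the claim (81%), the q-rule gives 7%, 25%, 38% and 50% as the share of differing taxa rises through 1%, 5%, 10% and 17.4%; a separate family of three gives 66%. The size of the loss is conditional on that share, on the correlation, on reading variability as SD, and on a common 0.5 SD effect among the taxa that differ. What does not depend on those inputs is that the q-rule lets unrelated taxa decide the cut-off for organisms named in advance. This is a mismatch between rule and power claim with a better option available; it does not make the analysis invalid.

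**What to change.** Before the data are seen, list the array taxa that represent *S. pneumoniae*, *H. influenzae* and *M. catarrhalis*, and test their abundance as a prespecified family with Holm adjustment at 0.05. If more than three taxa map to these species, either use that number in the adjustment or define one summary per species. Keep the p and q below 0.05 rule for the remaining taxa, labelled exploratory, and state in Data Analysis that the rule in 4.e governs them. Restate the Aim 2 power at the alpha and sidedness actually used, with the assumed within-pair correlation, and say that it may stay below 80%.

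The cost is wording only: no extra samples, arrays or visits. The statistical price is a separate 5% family-wise error for this small family.

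### The greater-than-80% power for each continuous predictor is a single-test figure; for taxa, which must also meet q < 0.05, power is lower unless about a fifth or more of them truly differ

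*Protocol*

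**What the plan says.** Protocol, section 4, item i (Data Analysis), Aim 2, sets the comparison. The cases are first sinusitis episodes "occurring among 50 randomly selected children who have one or more episodes of acute bacterial sinusitis". For the controls, "An additional 50 matched control cases of uncomplicated URI will be selected", matched on calendar time.

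The regression variables are demographic factors, season, the community metrics (richness, evenness, diversity) "as well as the relative abundance of all taxa detected (including sinopathogens"). On the analysis: "A term will be included to account for the paired structure of the data". The power statement then takes each continuous predictor in turn. A mean difference between groups "equal to 50% of the variability of that predictor" is said to be enough: it "will give us greater than 80% power to find a significant effect of the predictor". No multiplicity condition is attached.

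Section 4, item e (processing and interpreting the PhyloChip data) sets the rule for sinusitis versus no-sinusitis differences. There, community metrics and "taxon abundance will be determined by two-tailed" t-tests or ANOVA, with false-discovery adjustment by q-values. Only taxa with both p and q below 0.05 "will be considered statistically significant".

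**The concern.** The power statement and the significance rule do not match for taxa. A power of 80% at p < 0.05 says how often one test, taken alone, detects a given difference. Under a false-discovery rule the per-test threshold is set by the data and is usually much stricter, so the same difference is detected less often.

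The abundance of specific taxa is named in primary objective 2 beside the gross community features. A reader who relies on the stated power could take a taxon that misses q < 0.05 as evidence against a half-SD difference, when the design may well have missed it.

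**Working it through.** **Inputs from the protocol.** 50 pairs; an effect of 0.5 of the predictor's variability, read here as an SD; two-sided tests; p < 0.05 and q < 0.05 for a taxon. The protocol does not say whether the SD is that of the predictor or of the pair difference. It gives neither the within-pair correlation ρ nor the share π₁ of taxa that truly differ. These are treated as assumptions and varied.

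**Step 1: the stated figure.** For a paired t-test with standardised difference d, the noncentrality is d√50 on 49 degrees of freedom.
- 0.5 SD of the pair difference: d = 0.5, noncentrality 3.54, power 93% at p < 0.05.
- 0.5 SD of the predictor: d = 0.5/√(2(1−ρ)). Power is 69% at ρ = 0 and reaches 80% at ρ of about 0.23, where d = 0.404. At ρ = 0.5 it equals the first reading.

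So the figure above 80% can be reproduced, but as a single test at p < 0.05.

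**Step 2: the q < 0.05 rule.** The per-test threshold a at which the expected false-discovery proportion is 0.05 solves

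(1−π₁)·a / [(1−π₁)·a + π₁·power(a)] = 0.05,

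that is, a = 0.05·π₁·power(a) / [0.95·(1−π₁)].

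Example with d = 0.5 and π₁ = 0.01: a = 0.05 × 0.01 × 0.316 / (0.95 × 0.99) = 0.00017, and power at that threshold is 0.316. The threshold is about 300 times stricter than 0.05.

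**Step 3: average power per truly different taxon.**

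| Share that truly differ | d = 0.5 (93% at p < 0.05): threshold | d = 0.5: power at q < 0.05 | d = 0.404 (80% at p < 0.05): power at q < 0.05 |
|---|---|---|---|
| 1% | 0.00017 | 32% | 6% |
| 5% | 0.0016 | 58% | 24% |
| 10% | 0.0041 | 70% | 36% |
| 17% | 0.0084 | 78% | 48% |
| 20% | 0.011 | 81% | 52% |

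With d = 0.5, power passes 80% at a share of about 19%. With d = 0.404 it is still 77% when half of all taxa differ.

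**Step 4: sensitivity.** The Benjamini-Hochberg procedure does not estimate the null share and is slightly stricter. With d = 0.5 it gives 31%, 57%, 68%, 76% and 78% for the same shares, and passes 80% at about 24%. A simulation with 8,500 independent taxa gave 31%, 57%, 68% and 76% at shares of 1%, 5%, 10% and 17%. The result depends on the share of taxa that differ, not on their number, so detecting fewer than 8,500 does not by itself change it.

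**The case against.** Several points on the other side have weight.

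- **This is not an arithmetic error.** The stated figure reproduces on a paired reading. That stands: the fault is one of scope, a single-test figure applied where a stricter rule governs.
- **The power sentence does not name taxa.** It speaks of continuous predictors, and the sentence listing the variables leaves some doubt about which are predictors and which are outcomes. The q-value rule is attached to t-tests and ANOVA in another section. The mismatch therefore comes from reading two sections together. Even so, taxon abundance is a listed continuous variable, and the q-value rule is written for the same contrast between groups.
- **The shortfall is not large everywhere.** A reader might infer that taxon-level power is far below 80% whatever the truth. The documents do not support that. On the favourable reading it is 78% at a share of 17%, and with Benjamini-Hochberg 82% at 30% and 88% at 50%. A within-pair correlation above 0.5 would help further, although matching is on calendar time only and no correlation is given.
- **The preliminary data do not fix the share.** The 1,482 taxa found lower in adult chronic rhinosinusitis are 17% of the array's capacity of about 8,500. The analysis covers detected taxa, whose number is not given; with 5,000 detected, purely as an illustration, the share would be 30%. Taxa missed with 7 versus 7 samples would raise it too. Those data concern another disease and age group, so they settle the question in neither direction.
- **Ignoring the pairing would give still lower figures.** Such an analysis has only 70% power at p < 0.05. Using it here would mix in a different shortfall, so it is left out of the size given.
- **The protocol does not say how a non-significant taxon will be read, and a statistical analysis plan could carry the detail.** Both are fair. But the protocol itself fixes the power claim and the rule that it does not meet.

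**Conclusion.** The point holds with a stated condition. The greater-than-80% power is a single-test figure and cannot be carried over to taxa judged at q < 0.05. For taxa, average power is below 80% unless roughly a fifth or more of the detected taxa truly differ and the effect is 0.5 SD of the pair difference or something equally favourable. If single-test power is only just 80%, taxon-level power stays below 80% at every share examined, up to 50%.

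This rests on assumed shares, on reading variability as an SD, on an equal effect for every truly different taxon, and on independent taxa. Correlation between taxa would mainly make the realised power more variable. Richness, evenness and diversity carry little multiplicity burden and are not affected. False positives are not at issue, since the plan controls false discovery. What needs correcting is what a negative taxon result can be taken to mean.

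**What to change.** In the Aim 2 data analysis text:

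1. Label the greater-than-80% statement as single-test power at p < 0.05, and limit it to richness, evenness, diversity and any sinopathogen named in advance.
2. Say whether the variability is the SD of the predictor or of the pair difference and, if the former, what within-pair correlation is assumed.
3. For taxa, give the average power at q < 0.05, or the detectable difference under that rule, for a stated share of truly different taxa, preferably over a range.

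The cost is one restated figure, which becomes less favourable. No children, arrays or analyses are added.

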b) Overcoming variability of the nasopharyngeal microbiome. Characteristics of nasopharyngeal colonization vary according to a variety of factors including attendance at day care, season, age, recent illness, socioeconomic status, etc¹⁰. To overcome this variability and still have a valuable baseline specimens that will permit comparison with an illness specimen, we will obtain surveillance specimens at entry and 4 other times. The specimens obtained closest in time preceding the episode of URI will be used as the baseline comparator.

c) Overcoming frequency of asymptomatic colonization with respiratory viruses. To interpret relationships between respiratory viruses and clinical illness, it is important to consider that respiratory viruses are detected in children without respiratory symptoms. The frequency of asymptomatic infection varies with age: viruses are detected in ~15% of healthy school-aged children and up to 31% of healthy infants.^{29,30} We will perform surveillance viral diagnostics on nasal wash samples at entry and 4 other occasions to estimate the seasonal frequency of asymptomatic infections for our study population; this information will be used as a reference point in analyses of viral infections during periods of illness.

d) Definition of Sinusitis: The 3 clinical presentations of sinusitis detailed in C.3.c above are widely accepted by 5 national societies: the American Academy of Allergy, Asthma and Immunology, the American Academy of Otolaryngic Allergy, the American Academy of Otolaryngology – Head and Neck Surgery, the American College of Allergy, Asthma, and Immunology, and the American Rhinologic Society.¹⁷ The American Academy of Pediatrics and the Infectious Diseases Society of America are including these presentations in their new guidelines (in press and PI is an author). In 4 clinical studies it has been shown that by using these stringent criteria, sinusitis is diagnosed in only 7-8% of respiratory infections presenting to the pediatrician.^{3,4,6,7}

e) Feasibility of enrollment, follow-up and Phylochip analysis. Both the principal investigator and the co-investigators have conducted several longitudinal studies over several years of large numbers of participants (daycare, asthma, birth cohort)^{2,29,30}. Subjects were recruited from the same practice that is participating in this study. The use of experienced coordinators and tested strategies for retention has led to excellent rates of

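### The 80% power claimed for both Aim 2 comparisons does not follow from 50 matched pairs at two-sided 0.05; with no within-pair correlation it is about 70%

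*Protocol*

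**What the plan says.** The Aim 2 part of the Data Analysis section (4.i) takes the first sinusitis episode from each of 50 randomly selected children and adds 50 matched control episodes. Matching is on date only: "The controls will be chosen so that their uncomplicated URI closely matches the case of acute bacterial sinusitis in calendar time". The analysis is to respect this: "A term will be included to account for the paired structure of the data".

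Two power statements follow. For continuous predictors, a difference in means "equal to 50% of the variability of that predictor will give us greater than 80% power to find a significant effect of the predictor". On the binary side (detection of a sinopathogen, for example), the text reads: "we will have 80% power to detect the difference between the percent of sinopathogens present equal to 55% for the acute bacterial sinusitis group". The control rate is 30%. Neither statement comes with an alpha level, sidedness, a test, a within-pair correlation or a definition of variability.

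The only testing convention for these between-group comparisons is in section 4.e, on processing the PhyloChip data. Differences "in both gross community metrics (e.g. richness, evenness and diversity) as well as taxon abundance will be determined by two-tailed" t-tests or ANOVA, and taxa with p and q below 0.05 "will be considered statistically significant".

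**The concern.** A standard calculation for 50 per group at two-sided 0.05 falls visibly short of 80% at both stated effects. The 1:1 matching might close the gap, but only if pair members resemble each other enough, and the protocol neither assumes nor justifies any degree of resemblance.

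This comparison is the second primary objective. If true power is near 70%, the chance of missing a real difference of the stated size is about 30%, where the text implies 20% or less. A null result on sinopathogen presence or diversity would then look better supported than it is, and a reader cannot tell which assumption the 80% depends on.

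**Working it through.** **Inputs.** From section 4.i: 50 cases, 50 controls, 1:1 matching on calendar time, 55% versus 30%, and a difference of 0.5 units of variability (read first as the between-child SD). From section 4.e: two-tailed tests and a 0.05 threshold. That convention is stated for community metrics and taxa; applying it to the binary predictor is my assumption, by convention.

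**Step 1. Attempt to reproduce the stated figures, ignoring the pairing.**

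- Continuous: 0.5 × √(50/2) − 1.96 = 2.50 − 1.96 = 0.54, and Φ(0.54) = 70.5%. The t-test gives 69.7%.
- Binary, pooled z: mean proportion 0.425; null SE = √(2 × 0.425 × 0.575/50) = 0.0989; alternative SE = √((0.55 × 0.45 + 0.30 × 0.70)/50) = 0.0957. Then (0.25 − 1.96 × 0.0989)/0.0957 = 0.588, and Φ(0.588) = 72.2%. Unpooled z gives 74.3%, enumerated chi-squared 73.7%, Fisher 66.5%.

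No two-sided version reaches 80%. Replacing 1.96 with 1.645 (one-sided 5%) gives Φ(0.855) = 80.4% for the continuous claim (79.9% by t-test) and 81.9% for the binary claim. That match suggests a possible source for the figures but does not prove it.

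**Step 2. Paired analysis, continuous predictor.** With within-pair correlation ρ, the SD of the pair difference is √(2(1 − ρ)) between-child SDs. The noncentrality is √50 × 0.5/√(2(1 − ρ)) on 49 df. At ρ = 0 this is 2.50, and power is 68.8%.

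**Step 3. Paired analysis, binary predictor.** With within-pair correlation φ:

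- P(both positive) = 0.55 × 0.30 + φ√(0.55 × 0.45 × 0.30 × 0.70) = 0.165 + 0.228φ.
- At φ = 0 the discordant cells are 0.385 and 0.135, total 0.52.
- McNemar, normal approximation: Φ[(0.25√50 − 1.96√0.52)/√(0.52 − 0.25²)] = Φ(0.354/0.676) = Φ(0.524) = 70.0%.

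**Step 4. Range over the correlation (50 pairs, two-sided 0.05).**

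| Within-pair correlation | 0 | 0.1 | 0.2 | 0.3 | Value needed for 80% |
|---|---|---|---|---|---|
| Continuous, 0.5 between-child SD, paired t | 68.8% | 73.3% | 78.2% | 83.4% | 0.23 |
| Binary, McNemar normal approximation | 70.0% | 74.2% | 78.8% | 83.6% | 0.22 |
| Binary, asymptotic McNemar, enumerated | 72.6% | 77.1% | 81.8% | 86.6% | 0.16 |
| Binary, exact McNemar | 63.6% | 68.5% | 74.3% | 80.7% | 0.29 |

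**Step 5. Alternative meaning of variability.** If it is the SD of the paired differences, the noncentrality is 0.5 × √50 = 3.54 and power is 93.4%. This would satisfy the continuous claim. It has no bearing on the binary one.

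**Step 6. Detectable differences at 80% power, zero correlation.** Continuous: 0.57 between-child SD. Binary against 30%: 58.2% (normal approximation), 57.4% (asymptotic) or 59.9% (exact).

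**The case against.** The strongest reply is that the statements are under-specified rather than false. Alpha, sidedness and correlation are details a statistical analysis plan may supply. Zero correlation is the least favourable non-negative case: controls are matched closely on date, and the protocol itself notes that "Characteristics of nasopharyngeal colonization vary according to a variety of factors including attendance at day care, season, age, recent illness, socioeconomic status", so season should induce some resemblance within pairs. At correlations of 0.1 to 0.2, the paired t and the two non-exact McNemar calculations give 73% to 82%. The continuous claim also has a reading, the SD of paired differences, under which it is comfortably true. Finally, the regression will include age, day care and season. If the microbiota measure is the outcome, covariates explaining about 22% of its variance would lift 0.5 SD from 70% to 80% in an unpaired comparison.

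Part of this stands. Some positive correlation is plausible, 80% power is not impossible, and the continuous claim is easier to defend than the binary one. All figures above are unadjusted for covariates.

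The rest does not remove the problem. The protocol prints numerical powers, and a later plan would not correct them. Season is only one of the listed influences; day care, age, recent illness and socioeconomic status are not matched. The protocol gives no size for the within-pair correlation and no explained variance, and the covariate argument does not carry over directly if progression is the outcome. One-sided testing conflicts with the two-tailed tests specified for the community metrics and taxon abundance. No reading of what is actually written yields 80% for the binary claim.

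**Conclusion.** The concern holds. From the stated design of 50 cases and 50 matched controls, at two-sided 0.05 and with no within-pair correlation, power is about 70% for 55% versus 30% and 69% for 0.5 between-child SD. That is a shortfall of about 10 points, ranging from 7 to 16 points for the binary claim across McNemar versions. It closes if the within-pair correlation is roughly 0.2 to 0.3 (0.16 under the most favourable McNemar version), under a one-sided 5% test, or, for the continuous claim only, if variability means the SD of paired differences. The conclusion rests on carrying two-sided 0.05 over to the binary predictor and on unadjusted analyses. It is worth correcting because it concerns a primary objective, but it does not invalidate the design.

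**What to change.** In the Aim 2 power paragraph of section 4.i, state:

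- alpha and sidedness;
- whether variability means the between-child SD or the SD of paired differences;
- the paired test behind each power figure, since the binary result depends on the McNemar version;
- the assumed within-pair correlation and its basis.

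Then do one of two things:

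1. Restate power for 50 pairs: about 70% for both claims at zero correlation, with a short range (73% to 74% at 0.1, 78% to 79% at 0.2, 83% to 84% at 0.3, using the paired t and the normal-approximation McNemar).
2. Restate the differences detectable at 80% power with no correlation: about 58% versus 30% (57% to 60% by McNemar version) and about 0.57 between-child SD.

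The cost is rewording one paragraph. No further children, samples, chips or analyses are needed. The stated power becomes less favourable unless a within-pair correlation can be justified.
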